7.0 Expected Risks/Benefits

7.1 Expected Risks

- Patients: The risks to patients are those that could be associated with any unintended dissemination of personal health information. A member of the research team, with patient consent, will access their medical record and will hear an audio recording of the patients encounter, collected by the patient. We have highly secure procedures and extensive experience avoiding any breach of PHI, using encryption for audio recorders, a secure server space approved for research data storage, and removal of patient identifiers when no longer needed for tracking outcomes (at about 4 months post index visit).
- Clinicians: The risks to clinicians are those associate with any harm to reputation if they perform poorly and the encounter, captured on audio, were disseminated. We use encrypted audio, with data transfer directly to a secure research server space, and removal of identifiers when no longer needed for tracking.

7.2 – Expected Benefits

- Patients: We are conducting this study because we have prior evidence that indicates that patient have better health care outcome when clinicians address patient context in care planning. We hypothesize that providing contextual information via CDS will increase contextualization of care. Those patients in the intervention group may therefore receive better care. Those in the control group may also benefit from the exercise of completing a brief questionnaire that primes them to consider how their life challenges are impacting their health care.
- Clinicians: Participating clinicians will benefit from clinical decision support that provides them with information about any life challenges patients in the intervention group are experiencing that may be relevant to care planning. In addition they'll receive CDS about how to use the information in care planning efficiently. For patients in the control group, clinicians will receive usual CDS.

8.0 Data Collection and Management Procedures

- Patients: Data for this study will come from 3 patients sources: (a) Their medical record. These are contextual red flags (e.g. missed appointments, loss of control of a chronic condition); (b) a patient completed inventory that is tethered to their electronic medical record, eliciting both contextual red flags and contextual factors that are not likely to be present in the EHR. See appendix for items; (c) Audio recordings they collect of their encounter, from which contextual red flags and contextual factors will be noted, and whether the care plan is contextualized or contextual errors are present. The extraction of all these data follow the Content Coding for Contextualization of Care (“4C”) methodology as described in the proposal and previously published. These data will be accessible to the research assistant, project manager, and PI who are trained 4C coders, in a format that contains identifiers (MRNs). However, once they have extracted the data and paired data from the EHR with the audio coded data, identifiers are removed and replaced with arbitrary codes. They do retain, however, a crosswalk file between codes and MRNs separate from the research data so that they can follow up on patient chart based outcomes for the presenting red flag 4-6 months post index visit; once chart outcomes are extracted and tagged with the code, the crosswalk file will be destroyed. Beyond the coding team, data is only shared without identifiers. We will employ encryption on all audio recorders, and audio is immediately uploaded to a

secure research data approved server using a USB port following the visit. Access to the medical record is conducted by an RA trained in the “4C” method, as detailed in the proposal, which requires extracting specific information onto a spread – contextual red flags and factors as outlined in the research plan and detailed in our online and cited coding manual. In addition the patients note is linked to their data using a cross-walk file accessible only to the RA, project manager and PI, and then discarded after outcomes data is collected at 4-6 months, and identifiers are no longer needed.

- **Clinicians:** Encounters rather than clinicians are the unit of interest for this study. There will not be sufficient data collection from any individual clinician to draw inferences about his or her performance. In fact, clinicians are not randomized in this study. The same clinician will see patients in both the intervention and control groups, with and without contextualized CDS. He or she will also see USPs with and without clinical decision support. Hence, we plan only to collect aggregate data on the participating clinicians, including age range, years in practice, gender, and whether they are trained in internal medicine, family medicine or as advance practices nurses. As described directly above, the audio recordings by patients of their visit with their doctor or APN will be encrypted and stored on a secure server space. Their voices may be heard on audio, however, and recognizable. Encryption means that only the 4C coders and PI will have the capacity to hear the audio. As doctors are not a unit of study, we do not plan to keep the names of doctors associated with data from their visits. The audio files will be stored until the date of the completion of the study which will be four years from the start date. The digital files will then be irreversibly deleted.

9.0 Data Analysis

Hypothesis 1: CDS tools that inform clinicians of contextual factors and prompt them to ask questions when there are contextual red flags should result in a reduction in contextual error.

From real patient encounters (i.e. observational assessment): Each visit is “Content Coded for Contextualization of Care” (“4C”).⁶ 4C coding consists of reviewing the medical record and listening to the audio to identify the presence or absence of each of the four steps to contextualize care: Are there contextual red flags? If so, did the clinician probe them? If so, did the patient reveal contextual factors? Note that patients sometimes reveal contextual factors without a probe.³³ Regardless, did the clinician incorporate the contextual factor(s) into the care plan? 4C enables care plans to be classified as either contextualized or inappropriate because of a contextual error. In the latter instance, 4C also pinpoints the cause of the error as either secondary to a failure to probe a contextual red flag or failure to incorporate a contextual factor into the care plan. Hence, 4C coding will ascertain whether contextualized CDS is associated with a reduction in contextual error. And, when contextual error rates are reduced it will ascertain whether the reduction is associated with a higher probing rate or a higher rate of addressing contextual factors revealed without a probe into the care plan.

From USP encounters (i.e. experimental assessment): Does not require 4C coding; instead we use checklists based on evidence based criteria for appropriate vs inappropriate care. We will recruit USPs to present with 4 different scripts, with counterbalancing of control vs. intervention EHR rules and specific USP scripts among physicians, so that each physician sees 2 intervention USPs with the contextualized CDS rules

active and 2 control USPs with no contextualized CDS. As in our past work, likelihood of probing contextual red flags and contextualizing care will be tested using mixed effects logistic regression models to control for case differences and clustering of cases within physicians.

Hypothesis 2: Contextualized CDS predicts improved health care outcomes defined as a resolution of the contextual error after the index visit.

This analysis is based exclusively on data generated from the real patient visits: 4C coding has been extensively utilized to track the resolution of contextual red flags. We've demonstrated in a research setting that contextualizing care does predict improved health care outcomes as defined by resolution or partial resolution of the presenting contextual red flag at 6-9 months following the index visit (with the range depending on timing of follow up visit or scheduled tests).⁴ We propose to duplicate the methodology in this project, again tracking the status of the contextual red flags of patients seen at the index visit using a blind methodology, comparing those in the intervention group to the control. A detailed description of the process of scoring for outcomes based on contextualization of care is provided in the Content Coding for Contextualization of Care manual, publicly available.²⁷ As noted above, the outcome of interest is the disposition of the original contextual red flag when followed over time. The criteria for a good or poor outcome are prospectively determined, based on the original red flag, to avoid any bias resulting from knowledge of how the encounter gets coded. Determination of outcome is made blind to whether the index visit was coded as contextualized. A good outcome marks an improvement in the patient's condition as reflected in the contextual red flag. A poor outcome indicates no improvement in the contextual red flag.

Hypothesis 3: Contextualized CDS is associated with a reduction in misuse and overuse of medical services.

This analysis is based exclusively on data generated from the USP visits, in which physicians in the usual care and contextualized CDS groups see sets of "identical" patients for which misuse and overuse of medical services has been pre-defined. Utilizing our previously published methods,⁵ we will adopt the economic perspective of the patient and their third party payer, if any, with a time horizon of the expected consequences of care during the 30 days following the consultation. We consider only the direct consequences of care associated with diagnosis or misdiagnosis. We will not consider downstream costs beyond the initial recommendations from the consultation, and we will not consider societal costs not incurred by the patient or payer, such as lost productivity. We will include only resources related to the immediate diagnostic and therapeutic management at the index visit. Resources are direct medical costs in the case of unnecessary treatment and foregone direct medical costs in the case of under treatment.

Sample size calculations

Real patients (see Figure 5): Assuming, based on our prior research⁴ and data from the audit & feedback program,¹⁹ that contextual red flags with associated factors will be present in 50% of recorded visits, that 30% of patients approached will consent to participate, that physicians unaided will probe 50% of contextual red flags and that physicians unaided will contextualize care in 50% of visits with contextual factors, we propose to power the study for 80% power to detect an absolute increase in probe rate from 50% to 75% with contextualized CDS, and a corresponding increase in contextualization rates from 50% to 75%. Testing hypothesis 1 requires 58 patients with identified contextual factors per group, and therefore at least 145 patients consented and recorded per group. Testing hypothesis 2 requires at least 60 contextualized care plans in the intervention group and 60 non-contextualized care plans in the control group, which we expect to achieve with 80 identified contextual factors in the

intervention group (requiring 192 recorded visits) and 120 identified contextual factors in the control group (requiring 288 recorded visits). Thus, to test all project hypotheses, we will approach and consent a sufficient number of patients (approximately 1600) to obtain recordings of 480 patients, randomize them to the intervention and control groups on a 2:3 basis (192 intervention, 288 control), and expect to identify contextual factors associated with red flags in 80 intervention and 120 control patients. As the primary care clinics at the participating sites see approximately 5,000 unique patients (UIC) and 25,000 (Loyola) annually, accrual is likely to require no more than 4-6 months.

Sample size (USPs): In our past work with USPs, physician made contextual errors approximately 80% of the time.⁷ Assuming that the contextualized CDS enhances physician attention to red flags and leads them to probe substantially more often (e.g. increasing probe rate from 50% to 75%) and attend to identified information (e.g. increasing plan rate from 50% to 75%), we would expect overall contextual errors to occur no more than 45% of the time, and 28 control and 28 intervention USP visits would provide 80% power to detect such a difference and test hypothesis 1.

In our past work, we found an overall median cost of error of \$194 when cases presented with contextual red flags, based on a median cost of \$231 when contextual errors occurred and a median cost of \$0 when contextual errors did not occur.⁵ Based on bootstrapped simulation from our cost data in that study, 40 control and 40 intervention USP visits provide 83% power to detect the expected cost reduction (a median of \$156) due to reduced contextual errors using a Wilcoxon rank-sum test with a significance level of $p<.05$. Accordingly, we will conduct 40 control and 40 intervention USP visits to provide sufficient power to test both study hypotheses. As the study comprises 4 USP visits (2 control, 2 intervention) per physician, we will recruit 20 physicians for this portion of the study.

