2.0 Background/Scientific Rationale

A *contextual error* occurs when a care plan is inappropriate because of inattention to patient context.¹ Increasing the dosage of a patient's medication to manage deterioration of a chronic condition is a contextual error when the unaddressed underlying etiology is something in the patient's circumstances, such as a change in health insurance coverage, loss of social support or competing responsibilities. Contextual errors are a subtype of medical error as they reflect "...a wrong plan to achieve an aim."³

Our team has spent over a decade characterizing contextual errors (what they are and how to detect them), assessing their prevalence in various practice settings, measuring their impact on health care outcomes and costs, and trying to prevent them.^{8,9} For the latter we have attempted medical education interventions,^{4,18} and performance improvement strategies employing audit & feedback.¹⁹ A common theme of all of this work has been that contextual errors occur when physicians overlook essential information about patients' circumstances and behaviors when planning their care, with measurably deleterious consequences for both health care outcomes and costs.²⁰ Reducing contextual error rates may require real time strategies, activated during the clinical encounter, that prompt physicians to explore and address patient context in care planning.

In our research employing real patient collected audio we learned that contextual errors are common. In a study in which 601 patients carried concealed audio recorders into their visits across multiple practice sites, we found that contextual red flags were present in 403 of visits (67%), and that contextual factors were revealed in 208, meaning that in 35% of encounters effective care required identifying and addressing a contextual factor.⁴ Physicians were successful about 59% of the time, and responsible for a contextual error in the remaining 41%. In other words, about 14% (0.41 x 35%) of overall care was derailed by a contextual error. When we followed these patients for 9 months, the presenting problem at the time of the index visit was less likely to improve or resolve compared to visits without a contextual error (46% vs 71%; $P= 0.002$).

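### Real-patient Hypothesis 1 rests on patients with identified contextual factors, and membership of that set can depend on arm; add a comparison in a set fixed before randomization

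*Combined protocol and SAP*

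**What the plan says.** **Sample size (section 9.0).** The prevalence assumption is that "contextual red flags with associated factors will be present in 50% of recorded visits". The requirement for Hypothesis 1 is stated as "Testing hypothesis 1 requires 58 patients with identified contextual factors per group", and with 192 intervention and 288 control recordings the investigators "expect to identify contextual factors associated with red flags in 80 intervention and 120 control patients". Probing and contextualization are each assumed to rise from 50% to 75%.

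**Coding (section 9.0, Hypothesis 1).** "4C coding consists of reviewing the medical record and listening to the audio". The coder looks for a red flag, then a probe, then a revealed factor, and notes that some factors emerge unprompted. The last question applies with or without a probe: "Regardless, did the clinician incorporate the contextual factor(s) into the care plan". Not probing a red flag is listed as one of two causes of contextual error.

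**Earlier real-patient study (section 2.0).** There, "contextual factors were revealed in 208, meaning that in 35% of encounters effective care required identifying and addressing a contextual factor". "Physicians were successful about 59% of the time, and responsible for a contextual error in the remaining 41" percent.

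**Standardized-patient visits (section 9.0).** Clinicians with CDS are expected to probe more often and "attend to identified information (e.g. increasing plan rate from 50% to 75%), we would expect overall contextual errors to occur no more than 45" percent of the time.

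**Baseline data (section 6.0).** Before randomization every patient completes a questionnaire recording red flags and factors, and the answers are stored for both arms.

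**The concern.** The audio is recorded after randomization. A factor that is in neither the questionnaire nor the chart, and that the patient does not volunteer, can be coded only if the clinician probes. If CDS increases probing, more such factors are found in the intervention arm, and the two identified sets are no longer comparable by design. A difference in error rate between them then mixes the effect of CDS on care with its effect on who is counted.

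One of the two routes to benefit that the plan wants to separate, more probing, is the route that changes the set. A gain by that route could be partly or wholly missing from the contextual-error comparison, or the extra factors could shift the rate with no change in care.

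**Working it through.** **1. The plan's figure reproduces.** For 0.50 v 0.75, two-sided 0.05 (assumed; sidedness is not stated), 80% power, pooled variance, mean proportion 0.625:

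n = [1.96√(2 × 0.625 × 0.375) + 0.842√(0.25 + 0.1875)]² / 0.25² = 57.7, so 58 per group. The arithmetic is sound; the question is which set it applies to.

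**2. The two parts of Hypothesis 1 use different denominators.**
- Standardized patients: every scripted visit counts. 1 − 0.75 × 0.75 = 0.4375, which matches the stated ceiling of 45%.
- Earlier real-patient study: 208/601 = 34.6%, and 0.41 × 35% = 14% of all care. Errors were counted among visits with a revealed factor. Red flags were present in 403 visits, so 403 − 208 = 195 had a red flag and no revealed factor. The documents do not say how many of those had a factor that never came out.

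**3. How probing changes the set.** Suppose 50% of recorded visits truly have a factor (144 control, 96 intervention), none is documented beforehand, and every probed factor is revealed. Let v be the chance that an unprobed factor is volunteered (not given; assumed). The identified share is p + (1 − p)v, where p is the probe rate.
- v = 0: 50% v 75%, or 72 v 72 patients.
- v = 0.5: 75% v 87.5%, or 108 v 84.
- v = 1: 100% in both arms.

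The plan assumes equal yield: 120/288 = 80/192 = 41.7%.

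**4. Illustration of size.** Let s be the share of factors documented beforehand, r the chance that an undocumented factor surfaces, and c the share of identified factors addressed (0.50 v 0.75). Over all visits with a factor, the share addressed is c × [s + (1 − s)r]. With r = 0.50 v 0.75 (nothing volunteered):

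| s | Identified, control v intervention | Addressed, control v intervention | Difference (points) | Excess over 25.0 |
|---|---|---|---|---|
| 0% | 50% v 75% | 25.0% v 56.3% | 31.3 | 6.3 |
| 25% | 62.5% v 81.3% | 31.3% v 60.9% | 29.7 | 4.7 |
| 50% | 75% v 87.5% | 37.5% v 65.6% | 28.1 | 3.1 |
| 75% | 87.5% v 93.8% | 43.8% v 70.3% | 26.6 | 1.6 |
| 100% | 100% v 100% | 50% v 75% | 25.0 | 0 |

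Among identified factors the difference is 25.0 throughout. If half of unprobed factors are volunteered, r = 0.75 v 0.875. The excess is then 1.6 points at s = 50% (43.75% v 70.3%) and 0.8 at s = 75% (46.9% v 72.7%).

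**5. Direction.**
- With s = 50% and r = 0.50 v 0.60 (assumed), the figures are 37.5% v 60.0%, a difference of 22.5 points. The identified set overstates by 2.5. Break-even is an intervention r of 0.667.
- If CDS raises probing only, half of identified factors are addressed in both arms, and s and v are 0, the identified set shows 50% v 50% while all visits with a factor show 25% v 37.5%.
- If CDS changes nobody's care, but the extra factors found are addressed at 25% or 75% instead of 50% (s = v = 0), the intervention rate is (0.50 × 0.50 + 0.25 × 0.25)/0.75 = 41.7%, or (0.50 × 0.50 + 0.25 × 0.75)/0.75 = 58.3%. That is a spurious difference of −8.3 or +8.3 points.

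**6. Power in a set fixed before randomization** (0.50 v 0.75, two-sided 0.05, no allowance for clustering):

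| Share of the expected 80 and 120 | Intervention / control | Power |
|---|---|---|
| 100% | 80 / 120 | 0.953 |
| 75% | 60 / 90 | 0.879 |
| about 61% | 49 / 74 | 0.806 |
| 50% | 40 / 60 | 0.717 |

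**The case against.** The word *identified* comes from the sample-size text, not from a definition of an analysis set. The same text also speaks of visits in which factors are present, and section 9.0 codes every visit and treats not probing as a cause of error. Some unprobed visits may therefore count as errors, and the cited coding manual may settle which. This stands in part: it shows that the plan is ambiguous, not that it excludes every unprobed visit. But presence of a factor is still established by coding that uses the audio, and these documents do not say how an unprobed red flag with no revealed factor enters the denominator.

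A reader might infer that the plan understates the benefit of CDS, by up to 6.3 points. The documents do not support that. The figure needs no documented and no volunteered factors; section 6.0 makes the first unlikely and section 9.0 contradicts the second. It also attaches the 50% and 75% to identified factors only.

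A reader might take the 41.7% yield, set against 50% prevalence, as proof that factors go unseen. It also fits 50% with an allowance: 80/0.5 × 1.2 = 192, and 120/0.5 × 1.2 = 288.

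A reader might conclude that the fixed set should replace the 4C set as the sole primary. That would drop patients with a red flag but no documented factor, for whom probing matters most, and could leave about 72% power. Scoring every unaddressed documented factor as an error would also ignore the condition in section 1.0 that addressing it was feasible.

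**Conclusion.** The concern holds in limited form. As written, membership of the real-patient Hypothesis 1 comparison set can depend on arm, so the contextual-error comparison is not fully protected by randomization. Neither direction nor size can be established from the documents: they give neither the share of factors documented before the visit nor the share volunteered, and every figure in steps 3 to 5 of the working rests on assumed values for these. The effect is confined to factors not documented beforehand and is small if most are. The standardized-patient test is unaffected, and the probe rate would still show a gain in probing. The 58 per group is correct for the stated rates. If those rates hold among identified factors, power at 80 and 120 is about 95% before clustering.

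**What to change.** In section 9.0:

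1. Add a prespecified analysis, by assigned arm, of contextualized care among all randomized, recorded patients with a contextual factor documented before randomization (questionnaire, plus any in the pre-visit EHR). Keep the 4C definition of error, including feasibility. Report it beside the full 4C analysis, rest the Hypothesis 1 conclusion on the error rate on agreement between the two, and say in advance what counts as agreement.
2. Compare probe rates among patients with a red flag documented before randomization.
3. Report the number of identified factors by arm and by source (questionnaire, EHR, audio), and state how visits with an unprobed red flag and no revealed factor are classified. If the coding manual has the rule, quote it.
4. State the expected size and power of the fixed set, using the range in step 6 of the working. About 49 intervention and 74 control patients give 80%, roughly a quarter of recordings in each arm (49/192 and 74/288).

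**Cost.** No new data are needed. The fixed set is smaller, and may be mostly questionnaire factors, since section 8.0 describes the chart as a source of red flags. It omits factors first revealed at the visit, so it gives a protected comparison in a narrower group and does not recover the effect over all visits with a factor. That is why the full 4C analysis stays. When the questionnaire is completed on arrival, randomization must still follow it, as section 6.0 requires.

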3.0 Objectives/Aims

We will assess the potential of “contextualized CDS” to improve contextualization of care through a 27 month randomized controlled intervention trial, with assessment measures of both patient health care outcomes and averted costs associated with overuse and misuse of medical services. In addition to pursuing the aforementioned aim, the study design will adopt best practices for CDS design. We propose to implement highly personalized, concise, actionable contextual CDS strategies. The proposed study will pursue these aims by testing three hypotheses about contextualized CDS, and adhering to one design principle. The three hypotheses are that CDS:

1. *Reduces contextual error*: CDS tools that inform clinicians of contextual factors and prompt them to explore contextual red flags should result in a reduction in contextual error.
2. *Improve health care outcomes*: Contextualized CDS predicts improved health care outcomes defined as a partial or full resolution of the contextual red flag (e.g. elevated HgB A1c) after the index visit.
3. *Reduces avoidable health care costs*: Contextualized CDS is associated with a reduction in misuse and overuse of inappropriate or unnecessary medical services.

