10.0 Data and Safety Monitoring

We believe this study is minimal risk. However, to ensure the safety of research participants and to comply with NIH policies, a DSMB will be formed in early months of the project and given responsibility to review and approve study methods and analysis plan for the research. The DSMB will be organized by [name] and will consist of senior, experienced clinicians and health services researchers. If deemed necessary by the IRB, the Principal Investigators will not be on the Data Safety and Monitoring Committee, thereby ensuring some level of independent review. When necessary, we will bring in experts from outside the project to serve on the committee. The DSMB will review interim data mid-way through the study using a predetermined stopping rule to determine whether the intervention group is being significantly benefitted (or harmed) over the control group and whether early stopping is necessary. In the rare event that an adverse event attributable to the CDS intervention is found, we will contact the patient's provider and document in the chart the potential error that was found.

One mid-trial (half of patients enrolled) comparison of rate of 4-6 month post-visit resolution of visit contextual red flag for intervention vs. control visits using a mixed effects logistic regression model with random effect of clinic/site and fixed effect of trial arm. An effect of trial arm that is significant at the $p<.01$ level in either direction will trigger early stopping of additional recruiting (however, in patients already recruited who have completed the study visit, we will continue to obtain and analyze their 4-6 month post-visit medical records)

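### Hypothesis 2 is tested between randomized arms but sized on contextualized versus non-contextualized plans; power for the arm comparison is about 14-16% on inferred inputs

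*Combined protocol and SAP*

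**What the plan says.** Section 3.0 states hypothesis 2 as an effect of the intervention: "Contextualized CDS predicts improved health care outcomes defined as a partial or full resolution of the contextual red flag". Under Hypothesis 2, section 9.0 tracks red flags after the index visit, "comparing those in the intervention group to the control". Section 10.0 makes an interim comparison of the same outcome "using a mixed effects logistic regression model with random effect of clinic/site and fixed effect of trial arm".

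The sample size text in section 9.0 uses other groups: "Testing hypothesis 2 requires at least 60 contextualized care plans in the intervention group and 60 non-contextualized care plans in the control group". To fill these cells it plans 192 intervention and 288 control recordings, and the investigators "expect to identify contextual factors associated with red flags in 80 intervention and 120 control patients". Hypothesis 1 needs 58 patients with factors per group, "and therefore at least 145 patients consented and recorded per group".

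Table 1 in section 6.0 lists outcome tracking on 120 patients, which equals 60 + 60. Sections 1.0, 5.0 and 10.0 read as follow-up of all participants.

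**The concern.** The sizing contrast takes contextualized plans from one arm and non-contextualized plans from the other. It leaves out the expected 20 non-contextualized intervention plans (80 - 60) and 60 contextualized control plans (120 - 60). Membership depends on clinician behaviour after randomization, so the contrast is not a randomized comparison. It estimates the association between contextualized care and outcome, which is larger than any CDS effect that works by moving some plans from one category to the other.

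The 80 and 120 are themselves counts of factors found by 4C coding, which uses the visit audio as well as the chart. Entry to that set can therefore depend on probing, which CDS is meant to change.

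At stake is the reading of hypothesis 2. It accounts for 190 of the 480 recordings and for the unequal allocation, and its outcome drives the interim stopping rule. If the arm comparison is null, a reader who trusts the stated justification would take that as evidence against benefit when the trial could hardly have shown one.

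**Working it through.** **Inputs**
- Resolution 71% without and 46% with a contextual error: section 2.0, prior study. The hypothesis 2 text does not cite these rates; they are inferred.
- Contextualization 50% control and 75% intervention: section 9.0.
- Patients with factors: 80 v 120 as stated. Section 9.0 also assumes that "contextual red flags with associated factors will be present in 50% of recorded visits", which gives 0.50 x 192 = 96 and 0.50 x 288 = 144.
- Two-sided 5%: assumed. The documents give a significance level only for the standardized-patient cost test and, at .01, for the interim rule.

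**1. Reproduce the plan's 60 per group.** With pooled variance and 80% power,

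n = [1.96 √(2p̄(1-p̄)) + 0.842 √(p₁q₁ + p₂q₂)]² / (p₁ - p₂)²

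For 0.71 v 0.46, p̄ = 0.585, and n = (1.366 + 0.567)² / 0.0625 = 59.8, so 60. Power at 60/60 is 80.1%. The same formula for 50% v 75% gives 57.7, which matches the 58 stated for hypothesis 1. The sizing therefore fits the prior contextualization effect.

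**2. Source of the allocation.** 80 x 0.75 = 60 contextualized intervention plans, and 120 x 0.50 = 60 non-contextualized control plans. The 2:3 split fills these two cells. Hypothesis 1 alone needs 2 x 145 = 290 recordings.

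**3. Arm rates implied by the same inputs**
- Intervention: 0.75 x 0.71 + 0.25 x 0.46 = 64.75%
- Control: 0.50 x 0.71 + 0.50 x 0.46 = 58.5%
- Difference: 0.25 x 25 = 6.25 points

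**4. Power of the arm comparison.** At 80 v 120 the pooled rate is (51.8 + 70.2)/200 = 0.61. The standard error is 0.0704 under the null and 0.0698 under the alternative. Power = Φ[(0.0625 - 1.96 x 0.0704)/0.0698] plus the opposite tail = 0.140 + 0.002 = 14.2%.

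| Contextualization, intervention v control | Arm rates | 80 v 120 | 96 v 144 |
|---|---|---|---|
| 75% v 50% (plan) | 64.75% v 58.5% | 14.2% | 16.1% |
| 75% v 59% (section 2.0 rate in controls) | 64.75% v 60.75% | 8.7% | 9.5% |
| 84% v 59% (25-point gain kept) | 67.0% v 60.75% | 14.4% | 16.4% |
| 100% v 50% (ceiling) | 71.0% v 58.5% | 43.4% | 50.4% |

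The last row is the largest effect CDS can have through contextualization when controls are at 50%: 0.50 x 25 = 12.5 points.

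**5. All 480 recordings.** An undiluted 6.25 points at 192 v 288 gives 27.8%. Power of 80% is reached only if the 12.5-point ceiling applied undiluted to all 480, although factors are expected in only 200.

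**6. Precision.** From a control rate of 58.5%, the difference detectable with 80% power is 18.9 points at 80 v 120 and 17.3 at 96 v 144. The 95% confidence half-width is 1.96 x 0.0698 = 13.7 points at 80 v 120, and 12.5 at 96 v 144. To detect 6.25 points with 80% power at 2:3 would take about 793 intervention and 1,190 control patients with factors.

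**The case against.** **The 60 v 60 contrast may be the intended test.** No final test for hypothesis 2 is named. Section 9.0 proposes to repeat the prior study's methodology, which related contextualization to outcome, and Table 1's 120 fits 60 + 60. On that reading, size and test agree. The ambiguity is real, but this reading does not rescue the plan. If CDS changed nothing, and half the plans were contextualized in both arms, the contrast would compare 40 intervention plans (0.50 x 80) at 71% with 60 control plans at 46%. It would be significant about 70% of the time, with CDS credited for an effect it did not have. The sentence that proposes to repeat the methodology also specifies intervention against control.

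**The figures are conditional.** They rest on inferred rates, a causal reading of an observational association, CDS acting only through 4C-coded contextualization, no clustering, and two-sided 5%. Figure 5, which the sample size text cites, is not in the copy reviewed and could hold an arm-level calculation. All this stands, and 14-16% is not a fixed value. The mismatch between test and sizing needs none of these inputs, and no scenario at the expected factor counts exceeds about 50%. A CDS effect by another route would raise power, but no section quantifies one.

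**The consequences are limited.** Hypothesis 2 is not designated primary. Hypothesis 1 has about 95% power at 80 v 120, and the arm comparison does not itself inflate type I error. That is correct. The fault is confined to what hypothesis 2 can show and what readers are told about it.

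**Conclusion.** The concern holds. Hypothesis 2 is stated, and modelled at the interim, as a comparison of randomized arms. Its sample size, the 480 total and the 2:3 split rest on a contrast selected after randomization.

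Under the plan's own contextualization gain and the inferred 71% v 46%, the expected arm difference is 6.25 points rather than 25. Power is about 14-16%. Across the sensitivities at the expected factor counts it runs from about 9% to 50%, against the detectable difference of about 17-19 points. These figures assume that the prior association is causal, that CDS works only through contextualization, that follow-up is complete, and that clustering can be ignored. Missing outcomes would lower power further.

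**What to change.** - State that hypothesis 2 compares the randomized arms however the visit was coded, and name the final model.
- Replace the 60/60 justification with the power or detectable difference for that comparison at the expected set size, with its assumptions and a range.
- Report the arm difference with a 95% confidence interval, and say in advance that a null result will not exclude a useful effect.
- Label contextualized versus non-contextualized care as a secondary, non-randomized association.
- Name the analysis set. One option is patients whose red flags or factors were recorded before randomization, by questionnaire or in the chart. This avoids selection on probing, but omits flags first raised in the visit and may dilute the effect further.
- Make Table 1's 120 patients agree with follow-up of everyone in the chosen set. As a separate minor point, reconcile the 6-9 month window in Table 1 and section 9.0 with the 4-6 months given elsewhere.

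The cost is wording and a much less favourable stated power. No new patients or change of allocation are needed. If 120 is a real cap, chart abstraction grows by at most 360 on the 480 recordings (380 on the 500 patients in section 4.0). If all participants are already to be followed, it does not grow. The analysis set and follow-up rule should be settled before outcomes are abstracted.
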